5.5.2. Liver Chemistry Stopping Criteria

Liver chemistry stopping and increased monitoring criteria have been designed to assure subject safety and evaluate liver event etiology (in alignment with the FDA premarketing clinical liver safety guidance).
<http://www.fda.gov/downloads/Drugs/GuidanceComplianceRegulatoryInformation/Guidances/UCM174090.pdf>

Liver Chemistry Stopping and Increased Monitoring Algorithm

Liver Chemistry Increased Monitoring Algorithm with Continued Therapy for Alanine aminotransferase (ALT) $\geq 3x$ (Upper limit of normal) ULN but < 8xULN

Liver Safety Required Actions and Follow up Assessments Section can be found in [Appendix 2](#)

5.5.3. QTc Stopping Criteria

- The same QT correction formula must be used for each individual subject to determine eligibility for and discontinuation from the study. This formula may not be changed or substituted once the subject has been enrolled.
 - For example, if a subject is eligible for the protocol based on QTcB, then QTcB must be used for discontinuation of this individual subject as well.
 - Once the QT correction formula has been chosen for a subject's eligibility, the same formula must continue to be used for that subject for all QTc data being collected for data analysis. Safety ECGs and other non-protocol specified ECGs are an exception.
- The QTc should be based on single electrocardiograms obtained over a brief (e.g., 5-10 minute) recording period.

A subject who meets either of the bulleted criteria below will be withdrawn from the study:

- $QTc > 450$ msec
- $QTc > 480$ msec in subjects with Bundle Branch Block

5.6. Subject and Study Completion

A completed subject is one who has completed all phases of the study throughout the screening and treatment period to Visit 5 and completes the procedures for Visit 5. Any subject who withdraws prior to the completion of Visit 5 will be considered an early withdrawal. The end of the study is defined as the last subject's last visit.

6. STUDY TREATMENT

6.1. Investigational Product and Other Study Treatment

The term 'study treatment' is used throughout the protocol to describe any combination of products received by the subject as per the protocol design. Study treatment may therefore refer to the individual study treatments.

6.1.1. Study Medication Review and Return

All supplies must be returned at the end of the study and returned to GSK for destruction

6.1.2. Investigational Product Malfunction

An investigational product nasal spray that fails to function properly must be identified to GSK personnel for return to GSK for testing. Details of the failure will be documented in

the CRF. The subject should return the nasal spray to the clinic as soon as possible to avoid missing any doses. The site will then call the Registration and Medication Ordering System Interactive Voice Response System (RAMOS) and obtain a new treatment pack number for this subject and dispense a new study medication kit from the site's product supply, as instructed by the RAMOS.

	Treatment Products	
Product name:	Fluticasone furoate	Placebo
Formulation description:	0.05% w/w Fluticasone furoate in an aqueous suspension preserved with EDTA (0.015% w/w) and Benzalkonium Chloride (0.015% w/w).	An aqueous suspension to match the other study treatments minus the active component(s).
Dosage form:	Intranasal aqueous microsuspension	Intranasal aqueous microsuspension
Unit dose strength(s)/Dosage level(s):	Each spray=27.5 µg	N/A
Route of Administration	Intranasal	intranasal
Dosing instructions:	Inhale one spray in each nostril from each device in the morning	Inhale one spray in each nostril from each device in the morning
Physical description:	An amber glass bottle encased within a light grey plastic casing fitted with a white plastic side lever and white plastic cap. The device is a side actuated metering atomising spray pump filled with a uniform white suspension	An amber glass bottle encased within a light grey plastic casing fitted with a white plastic side lever and white plastic cap. The device is a side actuated metering atomising spray pump filled with a uniform white suspension
Device: Only use this when a medical device is used. Note that in most cases, an inhaler (e.g. Diskus, Ellipta) is not a device	Mistpro device with VP7 pump, white cap and white side actuating lever	Mistpro device with VP7 pump, white cap and white side actuating lever
Method for individualizing dosage:	Metered atomising spray pump	Metered atomising spray pump

6.2. Treatment Assignment

Subjects will be assigned to treatments for parallel group studies in accordance with the randomization schedule generated by Clinical Statistics, prior to the start of the study, using validated internal software.

Subjects (and subject's parent/guardian) will be educated at randomization prior to the first dose of IP regarding the use of the nasal sprays devices using a placebo demonstration device. Each subject will then be dispensed two treatment kits. Each kit will contain a nasal sprays device. One nasal spray device will be labelled Device A and the other Device B. Subjects (on their own or with assistance from parent/guardian) should administer one spray from Nasal Spray Device A into each nostril followed by one spray from Nasal Spray Device B into each nostril once a day in the AM. The first dose of study drug will be administered before 10 AM in the clinic on Visit 2.

Treatment Arm	Device A	Device A Dosing Instructions	Device B	Device B Dosing Instructions
FF 55µg QD	FFNS	Inhale one spray in each nostril from Device A in the morning	Placebo Nasal Spray	Inhale one spray in each nostril from Device B in the morning
FF 110µg QD	FFNS	Inhale one spray in each nostril from Device A in the morning	FFNS	Inhale one spray in each nostril from Device B in the morning
Placebo QD	Placebo Nasal Spray	Inhale one spray in each nostril from Device A in the morning	Placebo Nasal Spray	Inhale one spray in each nostril from Device B in the morning

Daily doses should be administered in the morning following pre-dose symptom assessment, the last dose will be administered on the morning of Visit 5. . Administration of the spray should be conducted according to the Patient Instruction Leaflet that will be provided to the sites by GSK. The subject Instruction Leaflets should be reviewed with the subjects (and /or subject's parent/guardian) and distributed to the subjects to take with them.

6.2.1. Assignment of Subject Number

At Visit 1, a unique **Subject Number** (CRF number) will be assigned by the site to any subject who has at least one Visit 1 procedure performed (other than informed consent) from a list of unique numbers provided by GSK. The unique subject number will be used to identify individual subjects during the course of the study.

6.2.2. Assignment of Randomisation/Treatment Pack Numbers

At Visit 2, subjects meeting the randomisation eligibility criteria will be assigned to study treatment via a telephone call to the RAMOS. During the call, the site will confirm the subject's **Subject Number** and the RAMOS will then assign two additional numbers:

1. **Treatment Kit Numbers** that identifies the double-blind medication to be dispensed to the subject from the investigators inventory; and
2. A **Randomisation Number** from the study randomisation schedule created by GSK. Once assigned, this number must not be reassigned.

6.3. Blinding

This will be a double blind study and the following will apply.

- The investigator or treating physician may unblind a subject's treatment assignment **only in the case of an emergency** OR in the event of a serious medical condition when knowledge of the study treatment is essential for the appropriate clinical management or welfare of the subject as judged by the investigator.
- Investigators have direct access to the subject's individual study treatment.
- It is preferred (but not required) that the investigator first contacts the Medical Monitor to discuss options **before** unblinding the subject's treatment assignment.
- If GSK personnel are not contacted before the unblinding, the investigator must notify GSK as soon as possible after unblinding, but without revealing the treatment assignment of the unblinded subject, unless that information is important for the safety of subjects currently in the study.
- The date and reason for the unblinding must be fully documented in the CRF

A subject will be withdrawn if the subject's treatment code is unblinded by the investigator or treating physician. The primary reason for discontinuation (the event or condition which led to the unblinding) will be recorded in the CRF.

- GSK's Global Clinical Safety and Pharmacovigilance (GCSP) staff may unblind the treatment assignment for any subject with an SAE. If the SAE requires that an expedited regulatory report be sent to one or more regulatory agencies, a copy of the report, identifying the subject's treatment assignment, may be sent to investigators in accordance with local regulations and/or GSK policy.

6.4. Packaging and Labeling

The contents of the label will be in accordance with all applicable regulatory requirements.

6.5. Preparation/Handling/Storage/Accountability

No special preparation of study treatment is required.

- Only subjects enrolled in the study may receive study treatment and only authorized site staff may supply or administer study treatment. All study treatments must be stored in a secure environmentally controlled and monitored (manual or automated) area in accordance with the labelled storage conditions with access limited to the investigator and authorized site staff.
- The investigator, institution, or the head of the medical institution (where applicable) is responsible for study treatment accountability, reconciliation, and record maintenance (i.e. receipt, reconciliation and final disposition records).
- Further guidance and information for final disposition of unused study treatment are provided in the SRM.
- Under normal conditions of handling and administration, study treatment is not expected to pose significant safety risks to site staff. Take adequate precautions to avoid direct eye or skin contact and the generation of aerosols or mists. In the case of unintentional occupational exposure notify the monitor, Medical Monitor and/or GSK study contact.
- A document describing occupational hazards and recommended handling precautions either will be provided to the investigator, where this is required by local laws, or is available upon request from GSK.

6.6. Compliance with Study Treatment Administration

Subject compliance with double blind study medication will be assessed at Visit 3, 4 and Visit 5, other clinic visits as specified in the Time and Events during treatment and Early Withdrawal by assessment of subject reported use on the e-diary. To ensure protocol adherence, a subject may be re-education from the study if their compliance with study treatment is <80%. And this no-compliance will be reported as protocol deviation.

6.7. Treatment of Study Treatment Overdose

An overdose is defined as a dose greater than the total doses described above which results in clinical sign or symptoms. GSK does not recommend specific treatment for an overdose. The investigator or physician in charge of the subject at the time will use clinical judgment to treat any overdose.

6.8. Treatment after the End of the Study

Subjects will not receive any additional treatment from GSK after completion of the study because the indication being studied is not life threatening or seriously debilitating and/or other treatment options are available

The investigator is responsible for ensuring that consideration has been given to the post-study care of the subject's medical condition, whether or not GSK is providing specific post-study treatment.

6.9. Concomitant Medications and Non-Drug Therapies

The concomitant medications related to Allergy Rhinitis diseases within 30 days prior to Visit 1 will be recorded in the CRF. All concomitant medications taken during the study will be recorded in the CRF. The minimum requirement is for the reporting of the generic drug name and dates of administration.

6.9.1. Permitted Medications and Non-Drug Therapies

Loratadine syrup, an on-the-count antihistamine, will be provided as rescue medication on only an as needed basis during the treatment period of the study. At Visit 2 after randomization, subjects will be dispensed rescue medication. The subject (and/or subject's parent/guardian) will record their daily use of allergy rescue medication, not to exceed **1 teaspoon (5 mL) with weight ≤30 kg or 2 teaspoon (10 mL) with weight >30 kg** a day. The use of rescue medication should be in accordance with the instructions provided with the medication.

6.9.2. Prohibited Medications and Non-Drug Therapies

Use of prescription or over-the-counter medication would significantly affect the course of AR, or interact with study drug are prohibited. Any non-drug therapies including nasal irrigation solutions are prohibited during the screening and treatment periods. All medications of the below are prohibited throughout the study from Visit 1 to Visit 5 or withdrawal Visit.

Medications
Short-acting antihistamines, including ocular preparations and antihistamines contained in anti-cold medicine, insomnia or antalgic.
Oral or inhaled anticholinergics
Oral or intranasal decongestants
Oral or antileukotrienes
Oral or inhaled long-acting beta2 agonists
Chinese traditional medicines that have potential effect to AR
Liquorice preparation
Medications that significantly inhibit the cytochrome P450 subfamily enzyme CYP3A4, including ritonavir and ketoconazole
long-acting antihistamines(eg. desloratadine, fexofenadine, cetirizine and loratadine[taken as rescue medication])
Intranasal antihistamines; or Intranasal or ocular cromolyh
Intranasal corticosteroids

Medications
Inhaled, oral, intramuscular, intravenous, ocular and/or dermatological corticosteroid (with the exception of hydrocortisone cream/ointment, 1% or less)
Immunosuppressive medications
Subcutaneous omalizumab
Chronic use of concomitant medications such as tricyclic antidepressants

7. STUDY ASSESSMENTS AND PROCEDURES

Protocol waivers or exemptions are not allowed with the exception of immediate safety concerns. Therefore, adherence to the study design requirements, including those specified in the Time and Events Table, are essential and required for study conduct.

This section lists the procedures and parameters of each planned study assessment. The exact timing of each assessment is listed in the Time and Events Table Section [7.1](#)

7.1. Time and Events Table

Table 2 Time and Events Table¹

Procedure	Visit Number					Early withdraw	Follow up
	1	2	3	4	5		
	Study Day						
Visit window (of days)	-4 to -14	1	8±2	15±2	29±2		5±2 days after subject's last dose
Informed consent ²	X						
Subject number assignment	X						
Medical history	X						
Verification of inclusion/exclusion criteria	X	X					
Skin testing / serum-specific IgE test (if not done within 12 months of visit 1)	X						
Clinical laboratory tests [Randomisation if applicable]	X				X	X	
12-Lead electrocardiogram	X				X	X	
Verification of randomized criteria		X					
Randomization number assignment		X					
Dispense double-blind study drug		X					
Dispense rescue loratadine		X	X ³	X ³			
Nasal spray technique education		X	X	X			
Collect study drug					X	X	
Review screening diary ⁴		X					
Review medical problem/medication diary ⁵		X	X	X	X	X	
Compliance assessment			X	X	X	X	
Review treatment diary ⁴			X	X	X	X	
Anterior rhinoscopy		X	X	X	X	X	
Investigator assess overall response to therapy				X	X	X	
Vital Signs	X				X	X	
Nasal examination	X	X	X	X	X	X	
Physical examination	X				X	X	

Procedure	Visit Number					Early withdraw	Follow up
	1	2	3	4	5		
	Study Day						
Visit window (of days)	-4 to -14	1	8±2	15±2	29±2		5±2 days after subject's last dose
AE/SAE review	X ⁶	←=====→				X	X
Concomitant medication review	X	←=====→				X	X

1. Parent/ guardian will record the symptom diary instead of subjects for all ages. The involvement of the parent/guardian in assessing and rating rhinitis symptoms may vary per subject. While it may not always be possible, the preference is for a consistent level of parent/guardian involvement throughout the study.
2. Informed Consent must be obtained prior to performing any Visit 1 procedures
3. The dispense will depends on as needed
4. The diary collects rTNSS, rTOSS, rescue usage and study medication usage
5. The diary collect **any** medical problem (other than AR) and any medications used
6. Serious AEs will be recorded from the time the consent form is signed until the follow-up visit. All AEs will be recorded from the start of study treatment until the follow-up visit.

7.2. Diary Recorded Information

Subjects (and/or subject's parent/guardian) will be provided with 3 diaries to record their allergy symptoms:

- A **screening diary** will be used during the screening phase (from Visit 1 to Visit 2) to capture the subjects' baseline symptom scores.
- A **daily treatment diary** will be used beginning on the first day of study medication administration (approximately 12 hours after the first dose at Visit 2) and throughout the remainder of the study.
- **Medical problem/medication diary** will be used during the study (from Visit 1 to Visit 5)

Screening diary and daily treatment diary will be used e-diary, both of them use the same 4-point, categorical scale of 0 to 3 to assess symptoms. Throughout the study, subjects (and/or subject's parent/guardian) will rate their nasal symptoms of AR and record them on a symptom diary. Parent/guardian will record the symptom diary instead of subjects for all ages. E-diary will be recorded approximately 12 hours after dose, include morning diary and evening diary, record time will be on every 6 to 10 morning and evening separately. The involvement of the parent/guardian in assessing and rating rhinitis symptoms may vary per subject. While it may not always be possible, the preference is for a consistent level of parent/guardian involvement throughout the study.

Subjects (and/or subject's parent/guardian) will also document study drug compliance and loratadine rescue medication use on the daily treatment diary. Additionally, subjects (and/or subject's parent/guardian) will record any medical problem (other than AR) they experience and any medications used on medical problem/medication diary.

7.3. Screening and Critical Baseline Assessments

All demographic and baseline assessments will be completed according to the Time and Events schedule in Section 7.1. Safety parameters physical exams, vital signs, electrocardiogram (ECG) and clinical safety laboratory assessments will be defined as baseline at Visit 1. Nasal exams baseline will be assessed at Visit 2.

Medical/medication history will be assessed as related to the eligibility criteria listed in Section 5. Height, weight, medical conditions will also be assessed at baseline. SAE information (see Section 12.3.2), if applicable, will also be assessed at baseline.

7.4. Efficacy

Electronic diary card will be used in this study to collect subjects (and/or subject's parent/guardian) rating efficacy endpoints, including rTNSS, rTOSS and rescue loratadine use.

7.4.1. Nasal Symptoms of AR

The nasal symptom endpoints for efficacy will be calculated from the daily subject-rated nasal scores. The four individual nasal symptoms that each subject will be assessed throughout the study are:

- Nasal Congestion
- Nasal Itching
- Rhinorrhea
- Sneezing

The total nasal symptom score (TNSS) is a composite score of the above four components with a maximum score of 12.

Rating

Subjects will use the following scale to assess the severity of each of the four symptoms above:

Rating Period

Using the 0 to 3 rating scale above, subjects will be instructed to score and document their symptoms in a reflective manner (rTNSS) using their diary.

- The reflective rating represents how the subject has been feeling over the preceding 12 hours. This assessment provides information on how effective the treatment is throughout the day and will be performed TWICE daily (AM and PM).
- The AM reflective assessment must be performed prior to administering the morning dose and assesses how the subject felt through the night.
- The PM reflective rating must be done approximately 12 hours after dosing but before bedtime and assesses how the subject felt during the day.
- The daily rTNSS is the average of the AM rTNSS and PM rTNSS assessments.

Table 3 Scoring of nasal symptoms

Severity (score) /symptom	None (0)	Mild (1)	Moderate (2)	Severe (3)
sneezing	Symptom is not present	sign/symptom is clearly present but minimal awareness; easily tolerated	definite awareness of sign/symptom that is bothersome but tolerable	sign/symptom is hard to tolerate; causes interference with activities of daily living and/or sleeping
rhinorrhea				
Nasal congestion				
Nasal itching				

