- The TNSS for each assessment time point is defined as the sum of the 4 individual nasal symptom scores for rhinorrhea, nasal congestion, nasal itching, and sneezing, and will range from 0 to 12. Each of the 4 individual nasal symptoms is evaluated by the subject using a 4-point (0 to 3) categorical scale and recorded on a diary card. The reflective scores (i.e., rTNSS) are ratings of the severity of symptoms over the previous 12 hours and are performed in the AM and PM. Daily (i.e., during one dosing interval) reflective scores are defined as the average of the PM reflective scores and the AM reflective scores of the next day prior to the AM dosing. For example, the Day 1 rTNSS will be computed as $[(\text{PM rTNSS})_{\text{Day1, first day of dosing}} + (\text{AM rTNSS})_{\text{Day2, prior to second dosing}}]/2$. And the Day 28 rTNSS will be computed as $[(\text{PM rTNSS})_{\text{Day 28, last day of dosing}} + (\text{AM rTNSS})_{\text{Day 29, last clinic visit}}]/2$.

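### Protocol and SAP disagree on who rates and who records the primary nasal symptom score, and nothing binding keeps one rater per child from run-in through treatment

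*Protocol*

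**What the plan says.** **On rating**, there are two descriptions.

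- *The subject rates.* Protocol 7.4.1: "The nasal symptom endpoints for efficacy will be calculated from the daily subject-rated nasal scores". SAP 11.6.4: "Each of the 4 individual nasal symptoms is evaluated by the subject using a 4-point (0 to 3) categorical scale".
- *The subject, the parent/guardian, or both rate.* Protocol 7.4 uses the e-diary to "collect subjects (and/or subject's parent/guardian) rating efficacy endpoints, including rTNSS, rTOSS and rescue loratadine use". Protocol 7.2 likewise says that the subject and/or parent/guardian "will rate their nasal symptoms of AR and record them on a symptom diary".

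**On recording**, there is a direct conflict.

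- Protocol 7.4.1, Rating Period: "subjects will be instructed to score and document their symptoms in a reflective manner (rTNSS) using their diary".
- Protocol 7.2: "Parent/guardian will record the symptom diary instead of subjects for all ages". Footnote 1 of the Time and Events Table (Protocol 7.1) says the same, and SAP 11.2.1 repeats that footnote.

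**On consistency**, Protocol 7.2 and the same footnote add: "The involvement of the parent/guardian in assessing and rating rhinitis symptoms may vary per subject", and then: "While it may not always be possible, the preference is for a consistent level of parent/guardian involvement throughout the study".

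**On capture**, footnote 4 of the Time and Events Table lists the diary content as the nasal and ocular scores, rescue use and study drug use. No rater item appears there, in the diary listing shells (SAP 11.15, Listings 20 and 21), in the primary model (SAP 7.1.2) or in the per-protocol checks (SAP 11.1.2.2).

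**The concern.** The primary endpoint is each child's treatment-period mean minus that child's 4-day baseline mean (SAP 11.6.4). Baseline comes from the screening diary and the rest from the treatment diary. If a parent judges severity in run-in and the child does so on treatment, or the reverse, the gap between their ratings becomes part of the change score. The same scores also decide entry, through the thresholds on average rTNSS and congestion in Protocol 5.3.

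As written, two sites could follow different sections and both be compliant. Enrolment starts at age 2 and at least 60 of about 120 children per arm are to be aged 2 to 6, so it is unclear how the subject-rated wording applies to the youngest. The study is descriptive and its product is point estimates with 95% CIs. What is at stake is the meaning of the score and the width of those intervals.

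**Working it through.** **1. Separate the two acts.** Recording fixes who enters the data; rating fixes who judges severity. Protocol 7.2 on the parent keeping the diary contradicts only the part of 7.4.1 that has subjects document their own scores. It does not say who rates. On rating, Protocol 7.4.1 and SAP 11.6.4 (subject) conflict with Protocol 7.2 and 7.4 (subject and/or parent/guardian).

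**2. Can a within-child switch occur?** The remark that involvement may vary describes differences between children, and those cancel in a within-child change. A switch within a child is possible because consistency over the study is only a preference that may not always be met.

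**3. Reproduce the plan's precision.** Protocol 9.2.1 gives SD 2.6 with 100 and 50 per arm.

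Half-width = t(0.975, 2n−2) × SD × √(2/n)

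- n = 100: 1.972 × 2.6 × √0.02 = 0.725 (protocol: 0.725)
- n = 50: 1.984 × 2.6 × √0.04 = 1.032 (protocol: 1.032)

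All ten entries of the table in Protocol 9.2.2 (SD 2.4 to 2.8) reproduce to three decimals.

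**4. Add rater switching.** The documents give neither a rating gap nor a switch rate, so both are assumptions. Let a proportion q of children switch fully at the start of treatment, with a gap of mean zero and SD τ on the 0-12 scale, independent of arm.

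SD′ = √(2.6² + q·τ²)

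| q | τ | SD′ | Half-width, n = 100 | Half-width, n = 50 |
|---|---|---|---|---|
| 0.1 | 1.0 | 2.62 | 0.730 | 1.040 |
| 0.1 | 1.5 | 2.64 | 0.737 | 1.049 |
| 0.1 | 2.0 | 2.68 | 0.746 | 1.062 |
| 0.2 | 1.0 | 2.64 | 0.736 | 1.047 |
| 0.2 | 1.5 | 2.69 | 0.749 | 1.066 |
| 0.2 | 2.0 | 2.75 | 0.767 | 1.091 |
| 0.4 | 1.0 | 2.68 | 0.746 | 1.062 |
| 0.4 | 1.5 | 2.77 | 0.772 | 1.098 |
| 0.4 | 2.0 | 2.89 | 0.806 | 1.148 |

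**5. Compare with the sensitivity table.** Its last row, SD 2.8, gives 0.781 and 1.111. Only one of the nine cells exceeds it. Passing SD 2.8 requires q·τ² > 2.8² − 2.6² = 1.08. That means q above 27% at τ = 2.0 and above 48% at τ = 1.5; at τ = 1.0 it cannot happen.

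**6. Bias.** If all switches moved scores the same way at the same rate in each arm, every arm mean would shift by q × shift and the expected difference between arms would not change. Bias needs unequal switch rates. As an illustration only, a 5-20 percentage-point imbalance with a 0.5-2 point shift gives 0.05 × 0.5 = 0.025 to 0.20 × 2 = 0.40. Nothing in the documents suggests such an imbalance.

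**The case against.** **The protocol saw the issue.** It anticipates varying parent involvement and asks for consistency, and the SAP carries the same footnote. That is true and softens the point, but a preference does not bind and no check is planned against it.

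**Excess variance is already watched.** Protocol 9.2.3 monitors the pooled SD blinded and allows a larger sample if it is much above 2.6. This covers variance from any source, including raters. However, the trigger is loose and the action discretionary, and without rater data the cause could not be identified.

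**The size is assumption throughout.** That stands. A partial or mid-period change would be diluted by averaging, and the SD of 2.6, taken from earlier paediatric studies, may already contain some switching.

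**Stronger readings that the documents do not support:**

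- *That switching is bound to go unseen.* The e-diary and eCRF specifications are not among the documents, so a rater field could exist. What can be said is that none appears in the places listed above.
- *That precision would fall outside what the sponsor considered.* That happens only in the most extreme assumed combination, and Protocol 9.2.2 is a sensitivity table, not a declared worst case.
- *That ages 2 to 6 are hit hardest.* No passage shows larger gaps or more switching there. With parents keeping the diary, a move to full self-rating by a very young child is arguably the least likely case. That subgroup simply has wider intervals to begin with.
- *That the treatment comparison is biased.* Randomisation and blinding argue against this.

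**Conclusion.** The contradiction is in current operative text of both documents and concerns the primary endpoint, so it holds whatever the numerical effect. The consequence is modest: some loss of precision and an unclear meaning of the score, with no expected bias between arms and no stated sample-size figure made wrong. Under the assumed ranges (gap SD 1.0-2.0, full switch in 10%-40% of children), half-widths grow by about 1% to 11% (SD′/SD = 2.62/2.6 to 2.89/2.6). The middle case moves 0.725 to 0.749 and 1.032 to 1.066. This is a low-cost improvement, not a threat to the study's conclusions.

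**What to change.** 1. Reconcile Protocol 7.1 (footnote 1), 7.2, 7.4 and 7.4.1 with SAP 11.2.1 (footnote 1) and 11.6.4, using one definition that states separately who rates and who records.
2. At Visit 1, name one rater per child (the parent/guardian in the youngest stratum) for every run-in and treatment entry. Allow a substitute only when that person is absent.
3. Record who rated each e-diary entry, unless this is already captured, and list switches by arm. This has to be prospective, because the rater cannot be reliably recovered later.
4. Optional: a supportive rTNSS ANCOVA limited to entries by the named rater. It selects entries on a post-randomisation feature, so it should stay supportive. It must also apply the minimum in Protocol 9.4.1 of 4 baseline days and 4 treatment days.

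Cost: wording changes in both documents, one extra diary item per entry, and slightly less flexibility for families. Because substitutes' scores still count, the primary analysis loses no data. Some switching can remain, but it becomes visible.
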